7.3 Nonclinical Studies

An extensive nonclinical program assessed the safety and absorption, distribution, metabolism, and excretion (ADME) and pharmacokinetic (PK) properties of amifampridine, including:

- Five safety pharmacology studies in central nervous system (rat), respiratory (rat), and cardiovascular (telemeterized dogs, *in vitro* human Ether-à-go-go Related Gene (hERG) and rabbit Purkinje fiber)
- Pharmacokinetics and mass balance in rat and dog
- *In vitro* metabolism in human and animal hepatocytes
- Human hepatic cytochrome P450 (CYP450) inhibition and induction
- Human P-glycoprotein (Pgp) interaction
- Single dose toxicity and toxicokinetic (TK) studies in mouse and rat
- Repeat dose toxicity and TK in rat (28-day, 13-week, and 2-year) and dog studies (28-day and 9-month)
- Reproductive and developmental toxicity in rat and rabbit
- Six *in vitro* and *in vivo* genotoxicity studies

The main nonclinical findings were CNS and autonomic nervous system (ANS) effects, the development of Schwannomas, and histologic changes in muscle tissues after administration of amifampridine.

7.4 Previous Clinical Studies

Amifampridine has been used for over 25 years in patients with multiple neurologic disorders including MG, LEMS, MS, CMS, ALS, congenital forms of nystagmus, and adult idiopathic nystagmus (AIN). There are a limited number of published controlled trials with amifampridine in these disorders. A review of the literature documents that amifampridine is a safe and effective treatment in multiple neurologic disorders and is recommended by the EFNS for first-line symptomatic treatment of patients with LEMS (Skeie, 2006; Skeie, 2010; Lindquist, 2011).

7.4.1 Amifampridine Phosphate in Healthy Subjects

A Phase 1 study with amifampridine phosphate was conducted to investigate the bioavailability/bioequivalence and tolerability of amifampridine administered as a phosphate salt or free base. In the first part of the study, a pilot tolerance study was conducted in 5 healthy male volunteers who received a single 10-mg dose of amifampridine phosphate to determine tolerability. In the second part of the study, bioequivalence testing was conducted in 27 healthy male volunteers. Each subject was randomized to receive either a single dose (2 × 10 mg tablets) of amifampridine as amifampridine phosphate or amifampridine base on one occasion and received the alternate treatment following a minimum of 72-hour washout period.

This study demonstrated bioequivalence for area under the plasma concentration-time curve from time 0 to infinity ($AUC_{0-\infty}$), with the 90% confidence interval (CI) for the base/salt ratio of 93.1% to 113.3% falling within the predefined limits of 80% to 125% for bioequivalence. The mean elimination half-life ($t_{1/2}$) values of amifampridine were 1.8 and 1.6 hours for the phosphate free base forms, respectively. Amifampridine peak serum levels (C_{max}) was 64.8 ng/mL for the phosphate form and 57.0 ng/mL for the free base form. Potentially higher solubility of the phosphate salt explained the slightly higher C_{max} observed for amifampridine phosphate compared with the free base. All adverse events (AEs) were mild or moderate, transitory and fully reversible. The nature and frequency of side-effects did not differ between the salt and free base forms. The most common AE (25 of 40 AEs) in 12 subjects was paresthesia, which was mainly minor peri-oral paresthesia. Since paresthesia is well recognized as an AE occurring in patients treated with amifampridine, all were considered as

possibly related to investigational product (IP) by the Investigator. The only other AE occurring in >1 subject and judged possibly related to amifampridine was abdominal pain (4 events). Flu-like symptoms (5 events) and feeling of discomfort (2 events) were also reported for > 1 subject in the study, however were considered not related to amifampridine treatment.

The only clinical laboratory test result abnormality reported in the study were minor, isolated, and reversible increases in aspartate aminotransferase (AST) and alanine aminotransferase (ALT), in a single subject after administration of 20 mg amifampridine base. Aside from this 1 subject no other laboratory abnormalities were observed. No electrocardiogram (ECG) abnormalities were observed. No deaths occurred in the DAPSEL study.

A Phase 1 open-label, randomized, single-dose, 2-treatment, 2-period crossover study in 46 healthy volunteers evaluated whether food consumption significantly affected the bioavailability of amifampridine phosphate tablets (LMS-001). Each subject received 20 mg amifampridine phosphate on 2 occasions, once fasting and once after consumption of a standard high fat breakfast. Each single 20 mg dose of amifampridine phosphate were administered 6 days apart. The results from this study indicate co-administration with food reduces exposures determined by C_{max} and AUC by approximately 40% and 20%, respectively. In addition, the time to maximum serum concentrations (T_{max}) was increased 2fold from approximately 38 minutes (fasted) to 78 minutes (fed). The drug was well tolerated with no serious adverse events and only 1 severe event, an episode of gastroenteritis unrelated to amifampridine. The most common AEs occurring in $\geq 10\%$ of subjects were: oral paresthesia (20 subjects; 43%), peripheral paresthesias (12; 26%), dizziness (5; 11%), headache (5; 11%), and oral hypoesthesia (5; 11%). Abdominal pain, nausea, peripheral paresthesias, dizziness, and headache were more commonly reported by subjects following administration of amifampridine phosphate in the fasted state. In humans, amifampridine is exclusively metabolized to a single major metabolite, 3-N-acetyl amifampridine, via N-acetyl transferases (NAT) (Catalyst internal in vitro and in vivo studies; data available upon request). There are 2 NAT enzymes, NAT1 and NAT2, both of which are principally hepatic and both of which are highly polymorphic. These allelic variations lead to slow and fast metabolic rates, which have been well characterized in the Caucasian and Asian populations, but somewhat less well in African populations (Sabbagh, 2006). Slow acetylators are estimated to comprise 50% to 59% of the Caucasian population, with the remainder being rapid acetylators (fast + intermediate). Fast acetylators are over represented in Asian population (92% of Japanese and 80% of Chinese) while they may be under represented in

African populations (25%) (Cascorbi, 1995). Slow acetylators will accumulate drug to higher levels (i.e. higher C_{max}) and clear drug more slowly (i.e. longer $t_{1/2}$), both of which may increase the risk of drug related toxicity (Fukino, 2008; Jetter, 2009).

7.4.2 Efficacy of Amifampridine

A Phase 3, randomized, double-blind, placebo-controlled study (LMS-002) evaluated the efficacy and safety of amifampridine phosphate (30-80 mg total daily dose) versus placebo in patients with LEMS. The change in QMG scores from baseline (Day 1, Part 2) to Day 14 (Part 3) reached statistical significance (p=0.0452), with the least square (LS) mean for QMG score increasing by 2.2 in placebo-treated patients, and increasing by 0.4 in amifampridine-treated patients. For the other primary endpoint, subject global impression (SGI), patients randomized to amifampridine on Day 1 reported, on average, that they were "pleased" (SGI mean \pm SD score of 5.9 ± 1.2) while on treatment. After being switched to placebo tablets, their opinions dropped, on average, 2.7 ± 2.3 points. The LS mean was -2.6 for the placebo group and -0.8 for the amifampridine group, a difference of 1.8 ± 0.6 (p=0.0028), corresponding to a patient assessment, of "mixed" for the placebo tablets. This substantial change in patients' assessments, to a worsening of their condition while receiving placebo, was considered clinically significant.

In addition to Study LMS-002, 5 randomized, double-blind, placebo-controlled studies and 1 double-blind study with an active comparator (reported in abstract form only) in 71 patients with LEMS are reported in the clinical literature. In all 6 studies, amifampridine (free base form) was shown to be more effective for the symptomatic treatment of LEMS compared with placebo or active comparator across a number of independent measures of neurological function. Supportive data from multiple published uncontrolled investigations and case reports demonstrate the long-term benefits of treatment with amifampridine in patients with LEMS, and show that discontinuation of amifampridine in a double blind controlled manner led to recurrence of underlying symptoms. Refer to the Firdapse Investigator Brochure (March 2019) for further details on these studies.

7.4.3 Safety of Amifampridine and Amifampridine Phosphate

Safety data collected from 1,454 patients or healthy volunteers in various studies (e.g. controlled study LMS-002, other controlled and uncontrolled published studies of LEMS or other neurologic conditions, a 3-year safety surveillance study (ATU), and PK studies) demonstrate amifampridine is well tolerated up to and including 80 mg/day (Firdapse Investigator Brochure, March 2019). The most common AEs observed from the clinical

safety data were perioral and peripheral paresthesias and gastrointestinal disorders (abdominal pain, nausea, diarrhea, epigastralgia). These events were typically mild or moderate in severity, and transient, seldom requiring dose reduction or withdrawal from treatment. In the pharmacogenomic study in healthy subjects (classified as either slow acetylators or fast acetylators), slow acetylators experienced >80% more drug-related AEs compared with fast acetylators (FIR-001).

Clinically significant or serious adverse events were infrequent in all studies for all indications. A total of 12 deaths were reported in the 1,454 patients or healthy subjects. Six of 12 deaths were associated with accompanying malignancy (1 of 6 with pulmonary embolus as terminal event), 1 due to tracheobronchitis, and 2 due to myocardial infarction (MI). Attribution to amifampridine for 2 of 3 deaths from the ATU study was specified as unrelated; causality for the third death was not reported. No attribution was specified in the academic series, but the author singled out the fatal MI as the only serious incident during amifampridine therapy, implying that the 2 deaths due to malignancy, the 1 due to malignancy and pulmonary embolus and the 1 due to tracheobronchitis were not related in his opinion. The author further states that no pathological findings related to amifampridine were found in the patient who died of tracheobronchitis. For 1 of the fatal MIs, the author speculates that a "sudden increase of physical activity" with amifampridine may have been a contributant (Lundh, 1984; Lundh, 1993); no causality was reported for the other fatal MI (Bertorini, 2011). Three deaths occurred in children with CMS, including 2 with fast-channel CMS (Beeson, 2005). Although no causal relationship was established with amifampridine, the authors advise its use cautiously in children and in fast-channel patients. The other CMS death was not thought to be related to amifampridine (Palace, 1991). Overall 7 of 12 deaths were not considered related to amifampridine; neither cause nor causality is known for 4 deaths; and amifampridine may have contributed indirectly to 1 of the MI-related deaths.

The most frequent clinically significant or serious event was seizure. Ten of 1454 (0.69%) individuals exposed to amifampridine experienced seizures. Electroencephalogram (EEG) findings, reported for 3 of the 10 patients, did not show epileptiform activity. Three of 10 seizures occurred in patients with LEMS (3/209; 1.44%), 4 occurred in patients with MS (4/774; 0.5%), 1 occurred in a patient with CMS (1/88; 1.14%) (Harper, 2000) and 2 seizures were reported in a literature-based study where both MG and LEMS patients were enrolled, but the paper did not state the indication (Sanders, 1993; Sanders, 2000; Flet, 2010; McEvoy, 1989; Boerma, 1995; Bever, 1996).

Three patients experienced seizures on a daily dose of ≥90 mg/day (LEMS or MG). No other cause was apparent in 2 cases; 1 patient had concurrent toxic serum levels of theophylline (McEvoy, 1989; Sanders, 1993). A fourth patient with LEMS had multiple seizures following accidental ingestion of 360 mg/day amifampridine for 7 days (prescribed dose 60 mg/day) (Boerma, 1995). There were potentially contributing conditions in 6 patients, specifically, concurrent treatment with theophylline (n=1; LEMS or MG), or coexistent brain metastases (n=1; LEMS), epilepsy (n=1; MS) and MS (n=4). In cases where follow-up was reported, most seizures did not recur with amifampridine dose reduction or treatment withdrawal. In the one accidental overdose case, seizures were controlled with intravenous clonazepam and the patient made a full recovery (Boerma, 1995). Note that a seizure rate of 4% can be expected in the natural course of patients with MS (Engelsen, 1997; Moreau, 1998; Kinnunen, 1987). Among the 774 MS patients treated with amifampridine included in the safety assessment of this report, 4 (0.5%) experienced seizures.

Other clinically significant or SAEs reported in more than 1 patient were palpitations (8/1,454; 0.56%), abnormal liver enzymes (6/1,454; 0.41%), QTc prolongation (2/1,454; 0.14%), and premature ventricular contraction/increased ventricular extrasystoles (2/1,454; 0.14%). Each of the following serious or clinically significant events was reported in a single patient: chorea, paresthesias, paroxysmal supraventricular tachycardia, cardiac arrest, druginduced hepatitis, gastroesophageal reflux, increased lipase and amylase, aspiration pneumonia with confusion, and urinary tract infection with confusion.

7.4.4 Overall Risks and Benefits

Data on amifampridine treatment in 1,454 patients or healthy volunteers support the favorable safety profile of amifampridine (both base and phosphate salt forms) at doses up to 80 mg per day. Current data demonstrate that amifampridine phosphate has an acceptable tolerability profile with a positive risk-benefit in patients treated with amifampridine. Refer to the Investigator Brochure (March 2019) for further discussion on benefit/risk of amifampridine.

7.4.5 Study Rationale

As discussed above in Section 7.4, a considerable amount of clinical experience is available with amifampridine and, in December 2009, amifampridine phosphate tablets (10 mg as free base), received marketing approval by the European Commission as Firdapse® for the symptomatic treatment of patients with LEMS. Case reports, animal data suggest that amifampridine may also have clinical utility in patients with SMA Type 3, providing

Page 25

symptomatic relief through its action on the impaired NMJ transmission. Thus, the purpose of this study (SMA-001) is to demonstrate the safety and efficacy of amifampridine in patients with Type 3 SMA.

8 STUDY OBJECTIVES

8.1.1 Primary Objectives

The primary objectives of the study are:

- To characterize the overall safety and tolerability of amifampridine compared with placebo in patients with SMA Type 3; and
- To assess the clinical efficacy of amifampridine compared with placebo in ambulatory patients with SMA Type 3 based on change from baseline in the Hammersmith Functional Motor Scale Expanded (HFMSE) scores.

8.1.2 Secondary Objective

The secondary objective of the study is:

 To assess the clinical efficacy of amifampridine compared with placebo by using the change from baseline in six-minute walk test, timed tests, and quality of life assessments;

9 INVESTIGATIONAL PLAN

9.1.1 Overall Study Design and Plan

This is a stratified, randomized (1:1), double-blind, placebo-controlled, , 2-treatment, 2-sequence, crossover, outpatient study designed to evaluate the safety, tolerability and efficacy of amifampridine in ambulatory patients diagnosed with SMA Type 3. The study will include about 12 male and female SMA Type 3 patients,

The planned duration of participation for each patient is at least 60 days excluding the screening period, which can last up to 14 days.

All patients who sign an informed consent will be screened for eligibility to participate in the study: inclusion and exclusion criteria; medical and medication history; complete physical exam (including height, weight); vital signs; standard 12-lead ECG, including QTc evaluation; clinical laboratory testing; serum pregnancy testing (females of childbearing potential only; result must be negative to proceed into the run-in period with open-label IP

administration); confirmed molecular diagnosis of SMA; and assessment of serious adverse events (SAEs) (Table1)

Table 1 Schedule of Events) conducted at the start of the Run-in period (Day 1, before starting medication) and during Run-in, until stable dose and frequency of amifampridine is established for at least 7 days, and at least a 3-point improvement in HFMSE score is achieved. Screening and the start of the Run-in period may be combined into a single visit, in which case overlapping procedures/assessments will only need to be performed once. On the last day of the Run-in period (Day 0), procedures/assessments, as detailed in Table 1 will be conducted to confirm eligibility for randomization, including a negative pregnancy test. Every attempt should be made to have the same individual perform all assessments for a patient throughout the study.

Randomized patients will be assigned to one of 2 treatment sequences under double-blind conditions, either placebo or amifampridine phosphate in Part 1, and then cross-over in Part 2 to receive the alternate medication which was not taken in Part 1.

Open-label Run-in

Amifampridine dose will be titrated upward every 3 to 4 days, starting at 15 mg/day, at the discretion of the Investigator. Patients will either visit or have telephone/video contact with the site for each dose titration and at least one in-person site evaluation at Week 3 of the Runin period. When the Investigator determines that the patient has reached the maximal tolerable and efficacious dose, the patient should demonstrate they can remain on a stable dose and frequency for at least an additional 7 days. The Open-label Run-in period may be extended if additional time is needed for the dose titration. At the end of this period, patients must show at least a 3-point improvement in HFMSE score from start of Run-in, to be eligible for randomization (Day 0).

Randomization

Patients who continue to meet all the inclusion and exclusion criteria will be randomized on the last day of the Run-in period (Day 0).

Period 1 (Days 1-14) (± 1 day for each of Days 7 and 14)

Patients who have successfully completed the Open-label Run-in and continue to meet all inclusion/exclusion criteria will be randomized (1:1 ratio) on Day 0 to receive either

Page 27

amifampridine tablets (10 mg as amifampridine phosphate) or placebo tablets for 14 days, under double-blind conditions, (blinded medication to start after assessments obtained on open-label medication, on Day 0). Test medication will be dispensed by the Catalyst designee, according to the randomization schedule provided by Sponsor. All unused medication and the container must be brought back to the study site at each clinic visit. Safety and efficacy assessments will be made, in the site clinic, on Days 7 and 14 as detailed in the Schedule of Assessments in Table 1 and Section 12 STUDY Procedures.

Period 2 (Days 15-28) (±1 day for each of Days 21 and 28)

Following the in-clinic assessments on Day 14 of Period 1, the Period 1 study medication is collected and the patient should be given the blinded Period 2 medication; either amifampridine phosphate or placebo tablets (whichever they did not receive in Period 1) for 14 days. The Period 2 medication is to start with the next dose after the assessments are performed on Day 14 with Period 1 medication.

Safety and efficacy assessments will be made, in the site clinic, on Days 21 and 28 as detailed in the Schedule of Assessments in Table 1 and Section 12 STUDY Procedures. All unused medication and the container must be brought back to the study site at each clinic visit, including on Day 28, which represents the end of the study.

Table 1 Schedule of Events

		Run-in			Period 1		Period 2	
Study Assessment or Event ^b	Screening Days -14 to -1	Start ^a Day 1	Week 3	Last Visit Day 0 end of Run-in	Day 7 ±1 day	Day 14 ±1 day	Day 21 ±1 day	Day 28 ±1 day
Informed consent c	X							
Inclusion/Exclusion Criteria	X			X				
Randomization				X				
Medical history	X							
Complete physical exam	X			X				X
Vital signs	X		X	X	X	X	X	X
12-Lead ECG and QTc evaluation	X			X				X
Clinical laboratory tests ^d	X			X				X
Pregnancy test ^e	X			X		X		X
Dispense blinded IP f,g				X		X		
IP accountability			X	X	X	X	X	X
Able to walk 30 meters	X							
INQoL or PEDSQL				X	X	X	X	X
HFMSE	X	X		X	X	X	X	X
Six-minute walk test				X	X	X	X	X
Time to rise from floor				X	X	X	X	X
Time to rise from chair				X	X	X	X	X
Time to climb 4 stairs				X	X	X	X	X
Time to walk 10 meters				X	X	X	X	X
Adverse events/SAEs h	X	X	X	X	X	X	X	X
Concomitant medications	X	X	X	X	X	X	X	X
Patient Dosing Diary Provided		X	X	X	X	X	X	

ECG = electrocardiogram; HFSME= Hammersmith Functional Motor Scale Expanded; IP = investigational product (amifampridine or placebo); INQoL = individual quality of life; PEDSQL = pediatric quality of life inventory; SAE = serious adverse event. *Footnotes continue on next page.*

^a Titrate from starting dose of 15 mg/day, every 3 to 4 days with at least one site visit at Week 3. Last week of run-in, study drug dose and frequency must be stable before being eligible for randomization on Day 0.

^b All safety assessments (vital signs, ECGs, laboratory tests) are to be performed before the dose taken in the study clinic unless specified otherwise. All efficacy assessments will be performed at standardized times relative to the dose that must be taken in the study clinic on Days 0, 7, 14, 21, and 28 according to the efficacy assessments schedule in Section 9.7.

^c Informed consent must be obtained before any study procedures are performed.

- ^d Clinical laboratory tests include serum chemistry, hematology, and urinalysis.
- ^e Serum pregnancy tests will be obtained from female patients of childbearing potential only at Screening; urine dipstick may be used for the remainder of the study.
- ^f IP will be administered by the clinic staff during in-clinic visit so assessments can be timed according to IP administration.
- ^g Patients will be provided blinded packages containing amifampridine or placebo depending on their randomized sequence of treatment. Collect all open-label medication.
- ^h SAE reporting commences when informed consent is signed. Non-serious adverse event reporting commences on Day 1 of run-in (Section 10).

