The investigational product (IP) is amifampridine, and it will be provided in round, white-scored tablets, containing amifampridine phosphate formulated to be the equivalent of 10 mg amifampridine base per tablet. Dosing is up to 80 mg/day in 3 or 4 divided doses.

The investigational product, and matching placebo, will be provided by Catalyst Pharmaceuticals, Inc., [name].

REFERENCE THERAPY, DOSE, ROUTE, AND REGIMEN:

The reference therapy is a placebo, provided as tablets indistinguishable from amifampridine tablets. The placebo will be administered consistent with the dose and dose regimen of the investigational product (amifampridine).

DURATION OF TREATMENT:

Approximately 8 weeks (depending on length of dose titration and excluding up to 14-day screening period). The Run-in phase requires that the patient must be on a stable dose and regimen of amifampridine for the last week of Run-in.

CRITERIA FOR EVALUATION:

Safety:

Safety will be assessed by the incidence of treatment-emergent adverse events (TEAEs), including serious adverse events (SAEs). Vital signs, 12-lead ECGs, clinical laboratory tests, physical examination, and concomitant medications will also be evaluated.

Efficacy:

Efficacy will be assessed by comparison of amifampridine versus placebo for:

Primary -

• Change from baseline in HFMSE total score;

Secondary -

- Change from baseline in quality of life assessments (INQoL or PEDSQoLTM).
- Change from baseline in 6-minute walk test.
- Timed items (rising from floor, rising from a chair, climbing 4 steps, walking 10 meters).

STATISTICAL METHODS:

Sample Size Determination

The sample size for this study is based on clinical considerations related to the epidemiology of the disease, and not on a formal statistical power calculation. The sample size should be representative of a sufficient number of patients to evaluate the study objectives (i.e. safety, tolerability, and evidence of efficacy of amifampridine in the target population). It is anticipated approximately 12 patients will be randomized.

Page 7

Safety Analysis

Safety analyses will be conducted on the safety population (i.e. all patients who receive at least 1 dose of amifampridine). The safety analysis will be descriptive and will be presented on observed data only.

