12.2 Open-label Run-in

Amifampridine dose will be titrated upward every 3 to 4 days, starting at 15 mg/day, at the discretion of the Investigator. Patients will either visit or have telephone/video contact with the site for each dose titration and at least one in-person site assessment at Week 3 of the Run-in period (Table 1). When the Investigator determines that the patient has reached the maximal tolerable dose, the patient should demonstrate they can remain on a stable dose and frequency for at least an additional 7 days. The Open-label Run-in period may be extended if additional time is needed for dose titration. At the end of this period, patients must show a ≥3-point improvement in HFMSE from start of Run-in, to be eligible for randomization (Day 0).

Patients should be given a Drug Dosing Diary to record each dose of their open-label medication and instructions on how to complete the form.

Additional visits are allowed as necessary. Screening visit and start of Run-in (Day 1) may be combined into a single visit.

12.3 Period 1

12.3.1 Day 0

Patients who are deemed eligible for continuation will have the assessments/procedures listed below completed on Day 0 after taking a supervised dose of their medication for that day during the clinic visit, so that the assessments can occur in the prescribed relation to the time of medication administration.

- Confirmation of Inclusion/Exclusion criteria;
- Assessment of AEs/SAEs;
- Complete physical exam with weight;
- Vital signs (seated position), including SBP, DBP, heart rate, respiration, and body temperature;
- Standard resting 12-lead ECG;
- Clinical laboratory tests including hematology, chemistry, and urinalysis;
- Urine pregnancy test in females of childbearing potential only;
- Concomitant medications;
- Collect patient Drug Dosing Diary and perform IP accountability of open-label medication;
- Efficacy assessments following in-clinic dose of open-label medication as listed below:

Order of Assessment at Each Study Visit (when applicable)	Start Time After Dose (+ 10 minutes unless otherwise specified)
HFSME	45 minutes
6-minute walk test	After HFSME
Time to rise from floor	After 6-minute walk
Time to rise from chair	After rise from floor
Time to climb 4 stairs	After rise from chair
Time to walk 10 meters	After climb stairs
Quality of Life Assessment	After 10-meters walk

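### With separate visits, the pregnancy test that clears a woman for open-label amifampridine can be up to 14 days old at first dose, and none is scheduled on run-in Day 1

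*Protocol*

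**What the plan says.** Protocol 9.1.1 lists the Screening procedures, among them "serum pregnancy testing (females of childbearing potential only; result must be negative to proceed into the run-in period with open-label IP" administration. Inclusion criterion 7 repeats the requirement for a negative serum test at Screening. Table 1 places Screening on Days -14 to -1, and 12.1 lets its procedures fall anywhere in those 14 days.

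On whether Screening and first dose coincide, 12.2 says: "Screening visit and start of Run-in (Day 1) may be combined into a single visit". This is permission, not a requirement. Table 1 shows run-in Day 1 as a visit of its own, with HFMSE, adverse events, concomitant medications and the dosing diary. Protocol 9.1.1 also refers to work "conducted at the start of the Run-in period (Day 1, before starting medication", so patients are seen before they take drug.

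The pregnancy-test row of Table 1 has four marks: Screening, Day 0, Day 14 and Day 28. Day 1 and Week 3 are blank. SAP Appendix 1, which has no Week 3 column, marks the same four visits. After Screening, footnote e says "urine dipstick may be used for the remainder of the study". At Day 0, 9.1.1 says procedures "will be conducted to confirm eligibility for randomization, including a negative pregnancy test".

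**The concern.** The first active dose is the first fetal exposure the trial can cause, and it rests on a result that may be two weeks old. The later step, blinded drug that is amifampridine or placebo in a 1:1 ratio, requires a negative test at the visit itself. The earlier step, open-label drug that is certain to be active and is titrated upward, does not.

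A pregnancy too early to detect at Screening, or conceived between Screening and Day 1, could be exposed to active drug until Day 0 before any scheduled test finds it. The Early Termination visit is written only into Periods 1 and 2 (12.3.2 and 12.4), so a woman who leaves during run-in has no further scheduled test. What is at stake is patient safety only; no efficacy or safety analysis uses the test.

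**Working it through.** **Inputs.** Screening on Days -14 to -1 (Table 1); combined visit optional (9.1.1, 12.2); pregnancy tests at Screening, Day 0, Day 14 and Day 28 (Table 1); two blinded periods of 14 days, 28 days in all (9.1.1). Total duration is given in two ways. The Synopsis has "Approximately 8 weeks (depending on length of dose titration and excluding up to 14-day screening period"; 9.1.1 has "The planned duration of participation for each patient is at least 60 days excluding the screening period, which can last up to 14 days".

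**1. The plan's own figure.** Days -14 to -1 are 14 calendar days, which matches the stated maximum Screening period.

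**2. Age of the result at first dose.** Day 0 is the end of run-in, so run-in Day 1 follows Day -1 directly. Subtracting the day labels would give 15 for a Day -14 sample; the correct count is 14.

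| Screening sample | Age at first dose |
|---|---|
| Day -14 | 14 days |
| Day -7 | 7 days |
| Day -1 | 1 day |
| Same day as first dose | 0 days |

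**3. Time from first dose to the next scheduled test.** Neither document states the run-in length. Total minus blinded days gives:
- 56 - 28 = 28 days from the Synopsis total;
- 60 - 28 = 32 days from the 9.1.1 total, which is a minimum.

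It can be longer: "The Open-label Run-in period may be extended if additional time is needed for the dose titration".

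**4. Longest gap between scheduled tests.** 14 + 28 = 42 days, or 14 + 32 = 46 days, before any extension.

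**5. What a Day 1 dipstick would add.** Let L be the Screening lead in days and d the extra days a urine test needs to turn positive compared with serum. The documents do not give d; I assume 0 to 4 days. The range of conception dates newly detectable on Day 1 is max(0, L - d):

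| L | d = 0 | d = 2 | d = 4 |
|---|---|---|---|
| 14 days | 14 | 12 | 10 |
| 7 days | 7 | 5 | 3 |
| 1 day | 1 | 0 | 0 |

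The gain is largest when Screening is early and close to nothing when it falls the day before.

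**The case against.** The strongest reply is that the plan breaks no rule of its own. Open-label drug does require a negative serum result, Screening is capped at 14 days, and nothing says a result inside that window has expired. The re-screening rule in 9.2.5, which lets other laboratory results stand for 30 days but not the pregnancy test, concerns carrying a result into a new Screening rather than its age within one. Section 12.2 contains no list of Day 1 assessments at all, so its silence proves little. All of this is fair. The point is a schedule weakness, not a contradiction; 9.2.5 is only supporting context, and the gap rests on the Table 1 row.

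There are also real safeguards: mandatory contraception (inclusion 7 and 9.5.2), exclusion of women planning pregnancy, site contact at each titration step, and an extra test at any visit where pregnancy is in question (9.6.4). They narrow the gap without closing it. Titration contacts may be by telephone or video, 9.6.4 depends on suspicion, and the protocol tests at Days 0, 14 and 28 despite requiring contraception.

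The expected number of cases is small. As an illustration with every input assumed, take 6 to 12 women of childbearing potential entering run-in, a conception risk of 1% to 20% a year, and 10 to 14 newly detectable days. The low end is 6 × 0.01 × 10/365, about 0.002 pregnancies; the high end is 12 × 0.20 × 14/365, about 0.09. Both use the 14-day lead for every woman, so shorter leads or combined visits lower them. That stands, and it limits the priority.

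Finally, a Day 1 dipstick misses conceptions in the last days before Day 1 and all those during a run-in of 28 days or more. That is correct, and the fix should not be presented as covering them.

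**Conclusion.** The concern holds as a low-priority patient-safety improvement. With separate visits, the negative result that permits open-label amifampridine is 1 to 14 days old at first dose, and no test is scheduled until Day 0. The age range follows directly from Table 1. The 28 to 32 days to the next test depend on a run-in length derived from the stated totals. The 10 to 14 days of newly detectable conception dates at the longest lead depend on the assumed urine lag of 0 to 4 days.

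Its importance is limited. It concerns only women of childbearing potential whose Screening and Day 1 are separate. Protocol 7.3 lists rat and rabbit reproductive and developmental studies, but the documents name no embryo-fetal hazard. No estimate or test in the SAP is affected.

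**What to change.** In Table 1 and 12.2, add a urine dipstick on run-in Day 1, before the first dose, for females of childbearing potential. Require a negative result to start open-label drug, and waive the dipstick when the Screening sample is taken that day. The newest result is then 0 days old at first dose in every case. A Week 3 dipstick would be an optional extra and is not part of this recommendation.

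The cost is one dipstick for each woman whose Day 1 is a separate visit. About 12 patients are to be randomized; the number entering run-in is not stated. The visit already exists, and footnote e already accepts dipsticks after Screening. It needs a minor protocol amendment; under 14.8, IEC approval is required first if the change is judged to influence patient risk or to need a revised consent form, at up to 3 sites. SAP Appendix 1 can be aligned at its next revision. The change helps only women who have not yet started run-in.
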